<Study protocol with SAP>

**Locoregional recurrence after neoadjuvant versus adjuvant chemotherapy
based on tumor subtypes in patients with early-stage breast cancer: A
multi-institutional retrospective cohort study**

(Brief Title: Locoregional Recurrence After Neoadjuvant Versus Adjuvant Chemotherapy)

Version 1.0

Document Date: 2022-04-22

1. Research Hypothesis and Objectives

: The hypothesis of this study is to investigate whether there is a difference in ipsilateral breast recurrence between patients who received preoperative chemotherapy and those who received postoperative chemotherapy after breast-conserving surgery and radiation therapy for breast cancer. The objective is to conduct a multi-institutional retrospective analysis to examine this difference.

2. Criteria for Selection and Exclusion of Study Subjects

*Selection Criteria:

- Patients who underwent breast-conserving surgery for invasive breast cancer at three hospital in Korea between 2004 and 2018.

* Exclusion Criteria:

- Patients who underwent mastectomy.
- Patients who did not receive pre- or postoperative chemotherapy.
- Patients who did not undergo radiation therapy.
- Patients with bilateral breast cancer.
- Male breast cancer patients.
- Patients with secondary cancer.
- Metachronous or synchronous cancers.

3. Number of Study Subjects

- 10328 patients

4. Specific Research Methods

- Retrospective analysis of clinical information and pathological findings of patients who underwent breast-conserving surgery at the hospital from January 2004 to December 2018.
- Confirmation of ipsilateral recurrence in all patients, noting the date of recurrence if applicable, or the date of last outpatient visit or death if no recurrence occurred.
- Assessment of significant differences in IBTR-free survival rates between patients who received neoadjuvant chemotherapy (NAC) and those who received adjuvant chemotherapy (CTx).
- Subgroup analysis based on patient age, molecular subtype (Luminal A, Luminal B, HER2-enriched, basal-like), and clinical-pathological characteristics.

- Survival analysis conducted using the log-rank test and Cox proportional hazards model, with calculations made within a 95% confidence interval.

5. Data Collection Items

- Patient information: Age at the time of surgery.
- Surgical information: Date of surgery, type of breast-conserving surgery.
- Pathological information: T stage, N stage, pathological complete response (pCR), hormone receptor status, HER2 receptor status, Ki-67%, histologic grade.
- Treatment information: NAC and chemotherapy regimen, hormone therapy, Herceptin administration.
- Prognostic information: Occurrence and date of local recurrence, occurrence date of other metastases or relapse, date of last outpatient follow-up

6. Informed consent

The requirement for informed consent was waived owing to the retrospective nature of the study.

7. IRB No.

- Seoul National University Hospital, 2204-074-1316
- Samsung Medical Center, 2023-09-076-001
- Boramae medical center, 10-2023-73

8. Statistical analysis plan

- Categorical variables are compared using Pearson's chi-square test.
- Continuous variables are compared using Mann-Whitney *U* and Kruskal-Wallis tests.
- Survival analysis would be conducted using the log-rank test with calculations made within a 95% confidence interval.
- Cox proportional hazards regression analysis are performed to adjust for related clinicopathological variables and estimate hazard ratios. Variables with a two-sided p-value of <0.05 in the univariate analysis would be included in the multivariate analysis, and those that showed a variance inflation factor of >4.0 in the multicollinearity test would be excluded. The model's goodness of fit was

evaluated using the Hosmer-Lemeshow test and a two-sided p-value of >0.05 indicated an appropriate model.

- The propensity scores are estimated using a logistic regression model, and 1:1 matching would be conducted using the greedy nearest-neighbor matching method without replacement using a caliper width of 0.10 standard deviation of the logit of the propensity scores. Variables that are differently distributed between the two groups were used for matching analysis. The standardized mean differences are calculated to evaluate the balance of variables between the two groups, and a value of <0.1 indicates an adequate balance.
- Missing data are treated using a complete case analysis approach.
- A two-sided p-value of <0.05 was considered significant.
- Analyses would be conducted using SPSS (version 26.0; SPSS Inc., IBM, Armonk, NY, USA) or R Statistical software (version 3.6.3; R Foundation for Statistical Computing, Vienna, Austria). Kaplan-Meier curves would be drawn using GraphPad Prism (version 10.0; GraphPad Software, San Diego, USA).
- The patterns of annual recurrence incidence would be drawn using the kernel smoothing method with the *ksmooth* function in R.

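### Both arms are selected on completed breast-conserving surgery, which can depend on chemotherapy response only in the NAC arm, so the planned hazard ratio may mix timing with selection

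*Combined protocol and SAP*

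**What the plan says.** Section 1 asks whether recurrence in the treated breast differs across two groups, described as "patients who received preoperative chemotherapy and those who received postoperative chemotherapy after breast-conserving surgery and radiation therapy for breast cancer".

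Section 2 selects "Patients who underwent breast-conserving surgery for invasive breast cancer at three hospital in Korea between 2004 and 2018". It excludes "Patients who underwent mastectomy" and "Patients who did not undergo radiation therapy". The rule is the same for both arms, and mastectomy after NAC is not treated separately.

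Section 4 makes the main contrast IBTR-free survival, NAC against adjuvant chemotherapy.

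Section 5 collects, as surgical information, "Date of surgery, type of breast-conserving surgery". Under pathological information it lists "T stage, N stage, pathological complete response (pCR), hormone receptor status", among other items. It has no item for the operation intended at diagnosis or for whether conservation was feasible then. It does not say whether stage in NAC patients is taken before or after chemotherapy.

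Section 8 plans Cox models with covariates chosen by univariate p<0.05, and 1:1 propensity matching, for which "Variables that are differently distributed between the two groups were used for matching analysis". It plans no sensitivity analysis for selection by operation, and no count of NAC patients who went on to mastectomy.

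**The concern.** The same entry rule acts at different points in the two arms. An adjuvant patient meets it before any chemotherapy, so her response cannot affect whether she is in the cohort. A NAC patient meets it after chemotherapy, so her response can.

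Two processes can follow in the NAC arm only:

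- **Selection on response.** Patients whose tumour responded poorly and who then had mastectomy drop out. Their counterparts in the adjuvant arm stay in. If poor response goes with higher IBTR risk, this favours NAC.
- **Enrichment for downstaged tumours.** Patients who were not candidates for conservation at diagnosis, but became so after NAC, come in. The adjuvant arm has no such patients. If their baseline risk is higher, this disfavours NAC.

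Because the two pull in opposite directions, neither a null result nor a difference could be put down to timing with confidence. The subtype analyses are exposed as well: if response or conversion varies by subtype, so does the selection.

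**Working it through.** **What can be reproduced.** The only relevant figure in the plan is 10328 patients. It comes with no effect size, power, event rate or arm split, so it cannot be re-derived, and this point does not depend on it. All inputs below are assumptions, and the true timing effect is set to none (HR 1.00).

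**Step 1: selection on response alone.** Assume 60% of patients respond, responders have half the IBTR hazard of non-responders, 90% of responders keep the breast, and a share k of non-responders do.

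- Mean hazard in the adjuvant arm: 0.6×0.5 + 0.4 = 0.70.
- Mean hazard in the retained NAC arm: m(k) = (0.6×0.9×0.5 + 0.4k)/(0.6×0.9 + 0.4k).
- k = 0.4: m = 0.43/0.70 = 0.614, HR = 0.614/0.70 = 0.88.
- k = 0.6: m = 0.51/0.78 = 0.654, HR = 0.93.
- k = 0.8: m = 0.59/0.86 = 0.686, HR = 0.98.

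A simulation of 2 million patients tested the mechanism with a different set-up: 60% good responders, doubled hazard in poor responders, and 30% of NAC operations depending on response. Keeping all starters gave 1.01. Keeping only conserved patients gave 0.95. The formula for that set-up gives [(0.6 + 0.4×0.7×2)/(0.6 + 0.4×0.7)]/(0.6 + 0.4×2) = (1.16/0.88)/1.40 = 0.94.

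**Step 2: enrichment alone.** If a share d of retained NAC patients were converted to conservation and carry h times the average hazard, HR = 1 − d + d×h.

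- d = 0.2, h = 1.25: 1.05.
- d = 0.3, h = 1.5: 1.15.
- d = 0.4, h = 2: 1.40.

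**Step 3: both together.** Steps 1 and 2 cannot simply be placed end to end. Converted patients are responders, so their hazard is 0.5×h, not h times the average. Counting them among the retained responders:

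HR = [m(k) + d×0.5×(h − 1)]/0.70

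- Lowest (k = 0.4, d = 0.2, h = 1.25): (0.614 + 0.025)/0.70 = 0.91.
- Near cancellation (k = 0.6, d = 0.2, h = 1.5): (0.654 + 0.050)/0.70 = 1.01.
- Highest (k = 0.8, d = 0.4, h = 2): (0.686 + 0.200)/0.70 = 1.27.

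**Step 4: a second model.** Let a share g of NAC starters be unsuitable for conservation at diagnosis and retained only if they respond well. Let p be the share of good responders, r the hazard of poor against good responders, and c the baseline hazard multiple of the unsuitable group. With A = p + (1 − p)r:

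HR = {[(1 − g)A + g×p×c]/[(1 − g) + g×p]}/A

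For g = 0.2 and 0.5, p = 0.5 and 0.7, r = 1.5 to 3 and c = 1.5 to 2, this runs from 0.92 to 1.30. The ends are:

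- g = 0.5, p = 0.5, r = 3, c = 1.5: A = 2, (1.375/0.75)/2 = 0.92.
- g = 0.5, p = 0.7, r = 1.5, c = 2: A = 1.15, (1.275/0.85)/1.15 = 1.30.

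**Step 5: what the planned analysis can reach.** NAC patients excluded for mastectomy are not in the data, so no model fitted to retained patients can bring them back. pCR cannot stand in for response, since it has no counterpart in the adjuvant arm. Enrichment is different: if T and N stage are pre-treatment, matching or adjustment on them would remove part of it. Post-NAC stage would not, because downstaging is what it records.

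**The case against.** **The question is already conditional.** Section 1 asks about patients who had conservation and radiotherapy, and IBTR is naturally studied in a conserved breast. Excluding mastectomy follows from the endpoint. This stands. A reader might infer that the comparison says nothing about timing, or that the plan claims to estimate the effect of choosing NAC. The documents support neither. However, the study title carries no conservation condition, and matched and adjusted hazard ratios for NAC against adjuvant treatment invite the wider reading.

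**Stage is collected and may be matched on.** This stands in part. A reader might infer that nothing in the plan touches the problem. That goes too far, because pre-treatment T stage would partly address enrichment. The gap is that Section 5 does not fix when stage is measured.

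**The size is assumed and may be small.** This stands. The documents give no response, conversion, mastectomy or event rates. For scale, assume 2% to 6% of the 10328 have events and 10% to 50% are in one arm. The HR detectable with 80% power, exp[(1.960 + 0.842)/√(D×a×(1 − a))] with D events and allocation a, is then 1.25 to 1.92, or 0.80 to 0.52 in the other direction. Response selection alone (0.88 to 0.98) lies inside that. Bias does not shrink with sample size, though, and it can mask a difference as well as create one.

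**Collecting feasibility for everyone is wasteful.** This stands. Adjuvant patients had conservation first, so the field would be almost uniformly positive. Only NAC charts need review.

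**Conclusion.** The asymmetry is real and follows from treatment order and the entry rule. It would vanish only if no NAC patient's operation depended on response, which the plan gives no means of checking. As written, the hazard ratio describes patients who reached conservation and radiotherapy, and may mix timing with two selection processes of opposite sign.

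The existence of the mechanism is well supported; its importance is not established. The joint range of about 0.91 to 1.27 assumes no timing effect, is unadjusted, and rests wholly on assumed response, retention and conversion figures. It is not the bias in the matched or adjusted estimate. A reader might take 0.88 to 1.40 as the span by joining the two separate ranges, but that ignores that converted patients are responders. A reader might also infer a known direction, and the documents support none.

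The study remains useful for its conditional question. The change should be made, but the cohort need not be abandoned.

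**What to change.** 1. For NAC patients, abstract pre-treatment clinical T stage or tumour size and, where recorded, whether conservation was judged feasible at diagnosis (yes, no, not recorded).
2. State in Sections 5 and 8 that the matching and Cox models use pre-treatment, not post-NAC, stage.
3. Pre-specify a sensitivity analysis comparing NAC patients who were feasible at diagnosis, or of comparable pre-treatment size, with the adjuvant arm. Report it beside the main result.
4. Report how many NAC patients were excluded for mastectomy, where hospital records allow.
5. Limit the conclusion to patients who completed conservation and radiotherapy, and say that it is not the effect of choosing chemotherapy before or after surgery.

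The cost is a chart review confined to NAC patients, though it reaches back to 2004 at three hospitals and will leave some values not recorded. The mastectomy count needs records from outside the defined cohort. The restricted analysis has fewer NAC patients and a wider interval. It deals with enrichment to the extent that feasibility or size is recorded; selection on response is reduced but not removed.

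### The full title features tumor subtypes, but no test of whether the NAC effect differs by subtype is specified, and subgroup results are not labelled exploratory

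*Combined protocol and SAP*

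**What the plan says.** The full title describes the comparison as "based on tumor subtypes in patients with early-stage breast cancer". Section 1 states a single overall hypothesis, "whether there is a difference in ipsilateral breast recurrence between patients who received preoperative chemotherapy" and those who received it postoperatively; subtype does not appear there.

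Section 4 lists "Subgroup analysis based on patient age, molecular subtype (Luminal A, Luminal B, HER2-enriched, basal-like), and clinical-pathological characteristics". The method it gives is "Survival analysis conducted using the log-rank test and Cox proportional hazards model", with 95% confidence intervals.

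Section 8 repeats the log-rank test and uses Cox regression for adjustment and hazard ratios. It also plans 1:1 propensity-score matching and sets one two-sided significance threshold of 0.05. Covariates enter the Cox model by two screens. The first is on univariate significance: "Variables with a two-sided p-value of <0.05 in the univariate analysis would be included in the multivariate analysis". The second drops collinear terms: "those that showed a variance inflation factor of >4.0 in the multicollinearity test would be excluded". Section 8 mentions neither subgroups nor subtypes. No section names an interaction or heterogeneity test, a multiplicity rule, or an exploratory status for the subgroup results.

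**The concern.** With subtype in the full title, readers will look for a statement on whether NAC carries a different recurrence risk in some subtypes than in others. That is a question about differences between effects, and no specified analysis addresses it. If the authors fall back on noting which subtypes reach p<0.05, the result depends partly on how many events each subtype contributes. A subtype with many events can be significant and one with few can miss, although the hazard ratio is the same in both.

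The smaller part of the concern is chance findings. With several subtypes examined under one unadjusted threshold and no exploratory label, a lone significant subtype could be read as confirmed.

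**Working it through.** The plan gives no power, event target, NAC share, subtype split or familywise error rate, so there is no figure of its own to reproduce. The omission was checked by reading every section. The arithmetic below shows what would follow if subtypes were tested separately, and what the proposed test could deliver.

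**1. Chance findings across four subtypes.** Inputs: four subtypes (Section 4) and alpha 0.05 two-sided (Section 8). Assumptions: one test per subtype and no NAC effect in any. Subtypes share no patients, so the tests are treated as independent.

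- P(at least one significant) = 1 - (1 - 0.05)^4 = 1 - 0.8145 = 0.1855, or 18.5%.
- At 0.05/4 = 0.0125 each: 1 - (1 - 0.0125)^4 = 0.0491, or 4.9%.

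**2. Why a pattern of p-values does not show different effects.** For a common hazard ratio and NAC share p, the expected z-statistic in subtype k is approximately |ln HR| × sqrt(d_k × p × (1 - p)), where d_k is the number of events in that subtype. It grows with the square root of the events. If two subtypes held 35% and 15% of events (assumed), their expected z-values would differ by a factor of sqrt(35/15) = 1.53 with identical hazard ratios.

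Even with equal information the pattern misleads. Assume one common effect, 80% overall power and four equally informative subtypes:

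- Overall expected z = 1.960 + 0.842 = 2.802; per subtype 2.802/2 = 1.401.
- Power per subtype = Φ(1.401 - 1.960) = 0.288.
- P(some significant, others not) = 1 - 0.288^4 - 0.712^4 = 1 - 0.007 - 0.257 = 0.736.

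Under these assumptions a mixed pattern appears about 74% of the time although the effect is the same everywhere. A mixed pattern is not itself an error; reading it as evidence of different effects is.

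**3. What an interaction test could detect.** With two treatment groups and four subtypes, the test has (2 - 1) × (4 - 1) = 3 degrees of freedom. Its power cannot be derived from the documents. One assumed case:

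- Events split 20/30/15/35% across subtypes; HR 2.0 in the subtype with 35% of events, 1.0 elsewhere; NAC share of patients 20% or 30%.
- NAC fraction of events in a subtype = p × HR / (p × HR + 1 - p). For p = 0.2 this is 0.4/1.2 = 0.333 where HR is 2.0, and 0.2 elsewhere. For p = 0.3 it is 0.6/1.3 = 0.462 and 0.3.
- Event counts were simulated as Poisson under constant hazards (40,000 runs). The likelihood-ratio statistic compared subtype-specific hazard ratios with a common one, against chi-square with 3 df at 0.05.

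| Total events (assumed) | NAC share 20% | NAC share 30% |
|---|---|---|
| 200 | about 39% | about 46% |
| 400 | about 68% | about 77% |

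So even a doubling of the hazard confined to one large subtype would often be missed at 200 events.

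**The case against.** The strongest defence is that the plan never undertakes to claim that effects differ. Its only stated hypothesis is overall, and the title's wording also fits reporting the comparison within each subtype, for which hazard ratios with 95% confidence intervals suffice. This stands in part. A reader might infer that every subtype will be tested at 0.05 and the p-values compared. The documents do not say so, and the 18.5% is therefore conditional, not the plan's error rate. Nor is it right that the planned methods cannot address the question: a Cox model can carry product terms. The accurate statement is that no such test is specified.

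A second defence is that multiplicity control across subgroups is optional in a retrospective cohort with one overall hypothesis. That also largely stands. An exploratory label would meet the point, and a 0.0125 threshold is a trade-off that the concern does not depend on. But the label is absent.

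A third is that the interaction test may be underpowered. It may, as the table shows. That argues for caution about subtype claims; it does not make separate p-values a valid substitute.

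**Conclusion.** The concern holds in this limited form: subtype is in the full title and four subtypes are to be analysed, yet the plan specifies no test of whether the NAC effect differs between them and does not label subgroup results exploratory. The missing test is the main gap; multiplicity is secondary.

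The 18.5% rests on one test per subtype, independence and no effect in any subtype. The 74% and the interaction-power figures rest on assumed inputs and are illustrations only.

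A reader might go further and conclude that the overall NAC comparison is undermined. Nothing here supports that: the point affects only inference about subtypes. The change should be made, because it is cheap and settles in advance how a subtype difference will be judged.

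**What to change.** In Sections 4 and 8:

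- Specify one 3-df likelihood-ratio test of NAC-by-subtype interaction in the adjusted Cox model, with the full cohort as the main subtype analysis.
- Repeat it in the matched cohort as a sensitivity analysis, checking covariate balance within each subtype. Overall balance after matching does not guarantee balance inside subtypes.
- Keep NAC, subtype and their product terms in that model whatever the univariate p<0.05 and VIF >4.0 screens show. Otherwise the screens could remove the terms being tested, since product terms are often collinear with their main effects.
- Report the four subtype hazard ratios with 95% confidence intervals from that model, and base any claim that the effect differs by subtype on the interaction test.
- Label within-subtype, age and other clinicopathological results exploratory.
- State that a non-significant interaction is not evidence of equal effects.

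The cost is SAP wording and one added model, fitted in the two cohorts. No new data should be needed: Section 4 already requires subtype, and Section 5 collects "hormone receptor status, HER2 receptor status, Ki-67%, histologic grade", from which it is presumably derived (the documents do not define it). The real downside is that fewer subtype claims will be supported, because the interaction test has limited power. How limited cannot be stated until event counts, NAC share and subtype split are known.

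### T and N stage have no stated time point and Section 8 does not restrict covariates to pre-treatment variables, so the between-arm models can use stage that is post-chemotherapy in the NAC arm only

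*Combined protocol and SAP*

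**What the plan says.** The comparison in Section 4 (Specific Research Methods) is between "patients who received neoadjuvant chemotherapy (NAC) and those who received adjuvant chemotherapy (CTx"). The exposure is therefore the timing of chemotherapy relative to surgery.

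T and N stage appear in one place, Section 5 (Data Collection Items): "Pathological information: T stage, N stage, pathological complete response (pCR), hormone receptor status, HER2 receptor status, Ki-67%, histologic grade". The item carries no time point and no marker separating clinical, pathological and post-treatment stage. Stage at diagnosis is not listed elsewhere. Section 4 gives the source only in general terms: "Retrospective analysis of clinical information and pathological findings of patients who underwent breast-conserving surgery". It does not say which of the two kinds of record supplies stage.

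Section 8 (Statistical analysis plan) has two routes to an adjusted comparison, and neither has a fixed covariate list.

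- The Cox model is to "adjust for related clinicopathological variables and estimate hazard ratios", with this selection rule: "Variables with a two-sided p-value of <0.05 in the univariate analysis would be included in the multivariate analysis".
- For the propensity score: "Variables that are differently distributed between the two groups were used for matching analysis". Balance is then judged by the standardized mean difference (SMD), where "a value of <0.1 indicates an adequate balance".

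Neither rule mentions when a variable is measured.

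**The concern.** Surgical stage means different things in the two arms. In adjuvant patients it precedes chemotherapy. In NAC patients it follows chemotherapy and may already reflect response. Matching or adjusting on it would pair downstaged NAC patients with adjuvant patients who had low stage from the start. Stage at diagnosis is a likely confounder of this comparison, so part of its effect would pass into the hazard ratio.

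The selection rules give no protection. Stage that differs between arms or predicts recurrence qualifies whenever it was measured. So would pCR, which sits in the same list and exists only after NAC.

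The SMD check looks at stage as recorded. If recorded stage is post-chemotherapy in one arm, balance on it says little about balance at baseline.

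**Working it through.** The plan gives no event rate, stage distribution, NAC share or effect size, so there is no figure of its own to reproduce. Its 10,328 patients do not enter the formula below. **Every input here is an assumption, chosen to show direction and rough size.**

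**Inputs.** True NAC hazard ratio 1.00. Baseline T1/T2/T3: NAC 25/60/15%, adjuvant 60/37/3%. Node-positive: NAC 59%, adjuvant 33%. T and N are independent, events are rare, and prognosis follows baseline stage. The prognostic hazard ratio is *h* per T level and *k* for node-positive, with (*h*, *k*) = (1.2, 1.3), (1.4, 1.5) or (1.7, 1.9). NAC lowers T by one level in a share of T2 and T3 patients and clears N in a share of node-positive patients: none, 20%/15% or 40%/30%.

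**Formula.** Let M_T = p1 + p2·h + p3·h² and M_N = 1 + q(k − 1), where p1 to p3 are the T shares and q the node-positive share. After matching on surgical stage, adjuvant patients have the NAC arm's surgical distribution, and for them that is baseline stage. So

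matched HR = [M_T · M_N at NAC baseline stage] / [M_T · M_N at NAC surgical stage].

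**Worked case: (1.4, 1.5), downstaging 40%/30%.**

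- NAC baseline: M_T = 0.25 + 0.60 × 1.4 + 0.15 × 1.96 = 1.384; M_N = 1 + 0.59 × 0.5 = 1.295; product 1.792.
- Adjuvant baseline: M_T = 0.60 + 0.37 × 1.4 + 0.03 × 1.96 = 1.177; M_N = 1 + 0.33 × 0.5 = 1.165; product 1.371.
- Crude HR = 1.792 / 1.371 = 1.31.
- NAC surgical stage: T1 = 0.25 + 0.4 × 0.60 = 0.49; T2 = 0.6 × 0.60 + 0.4 × 0.15 = 0.42; T3 = 0.6 × 0.15 = 0.09; node-positive = 0.59 × 0.7 = 0.413.
- M_T = 0.49 + 0.42 × 1.4 + 0.09 × 1.96 = 1.254; M_N = 1 + 0.413 × 0.5 = 1.2065; product 1.513.
- Matched HR = 1.792 / 1.513 = 1.18.

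**All cases.**

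| | (1.2, 1.3) | (1.4, 1.5) | (1.7, 1.9) |
|---|---|---|---|
| Crude | 1.17 | 1.31 | 1.53 |
| Matched, no downstaging | 1.00 | 1.00 | 1.00 |
| Matched, 20%/15% | 1.05 | 1.09 | 1.14 |
| Matched, 40%/30% | 1.11 | 1.18 | 1.30 |

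**Balance.** In this model recorded stage matches exactly (SMD 0.00). For unrecorded baseline T at 40%/30%, coded 0, 1, 2, the means are 0.90 and 0.60 and the variances 0.39 and 0.42, so SMD = 0.30 / √0.405 = 0.47. For N it is 0.177 / 0.492 = 0.36. At 20%/15% the values are 0.23 and 0.18.

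**Bias from the matching itself.** Give both arms the adjuvant baseline mix, so the crude HR is 1.00. At (1.4, 1.5) and 40%/30%, NAC surgical T becomes 74.8/23.4/1.8% and node-positive 23.1%. The surgical product is 1.111 × 1.1155 = 1.239, and the matched HR is 1.371 / 1.239 = 1.11.

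**A differently built check.** Sixty simulated cohorts of 10,328 per scenario used a single three-level stage (40/45/15%), NAC probability 8/25/55% by stage and a true HR of 1.00. Matching on recorded stage gave mean HRs from 1.05 (hazard 1.3-fold per level, 30% downstaged) to 1.49 (2.0-fold, 70%). Matching on pre-treatment stage gave 0.97 to 0.98.

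**The case against.** The strongest reply is that this is an ambiguity, not an error. Section 5 is a list of fields, not of definitions. The same item holds receptor status, HER2, Ki-67 and grade without naming a specimen, so its label alone does not fix stage to the surgical specimen. Section 4 names clinical information as a source, and an analyst may well take clinical stage for NAC patients. This stands. A reader might infer that the study matches on post-chemotherapy stage; the documents leave the time point open and do not support that.

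Three further points limit the claim.

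- **The balance check.** A reader might infer that it cannot reveal the problem. The model above has no T0 category, although the plan collects pCR. Complete responders could form a NAC-only T0 group, which might fail to match and would be visible in a stage-by-arm table. So the check need not reveal the problem, but other output might. The bias with T0 included was not calculated and could be larger or smaller.
- **How much confounding remains.** A reader might infer that baseline stage stays wholly uncontrolled. At (1.4, 1.5), matching moves the HR from 1.31 to 1.09 at 20%/15%, removing about 69% of the confounding on the log scale (1 − ln 1.086 / ln 1.307). At 40%/30% it removes about 37%.
- **The remedy.** Clinical stage carries its own error. If clinical T moves to an adjacent level and N flips, each with 10% probability in both arms, the HRs are 1.05, 1.09 and 1.14, no better than surgical stage at 20%/15%. At 20% error they are 1.09, 1.16 and 1.25, only slightly better than at 40%/30%.

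None of this answers the open selection rules, which admit post-treatment variables whichever stage was abstracted.

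**Conclusion.** The concern holds as a gap that permits bias, not as proof of bias. Section 5 does not say when T and N are measured, and Section 8 does not keep post-chemotherapy variables out of a comparison whose exposure is chemotherapy timing.

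Under the permitted reading, and if prognosis follows baseline stage, the illustration puts the error against NAC: a true HR of 1.00 appears as about 1.05 to 1.14 with 20%/15% downstaging, 1.11 to 1.30 with 40%/30%, and 1.00 with none. If post-treatment stage also carries prognosis, the size would differ. These ranges rest on assumed stage mix, downstaging and prognostic strength, and post-NAC T0 was not modelled. They should not be read as an estimate for this study. Nor do the documents say which hazard ratio would be affected as the main one, because they do not rank the Cox and matched analyses.

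This should be fixed. Confidence is medium, because the answer depends on a time point that the plan does not state.

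**What to change.** **Section 8.** Restrict the between-arm propensity score and Cox model to variables measured before any treatment. Include pre-treatment T and N in both, whatever their p-value or imbalance. Keep post-NAC T and N and pCR for analyses within the NAC arm.

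**Section 5.** Define T and N for NAC patients as stage at diagnosis. State whether adjuvant patients use surgical stage, which is already pre-chemotherapy, or clinical stage. Report the other as a sensitivity analysis where both exist.

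**Cost.** The Section 8 change is wording only. If NAC patients are already staged at diagnosis, so is the Section 5 change. Otherwise it needs chart abstraction, mainly for NAC patients. The documents do not show how often diagnosis stage can be retrieved, and the complete-case rule in Section 8 would drop patients without it.

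Residual confounding from clinical staging error remains. With diagnosis stage in the NAC arm and surgical stage in the adjuvant arm, (1.4, 1.5) gave HRs of 0.98 to 1.09 over the error patterns tried (N under-called in 10 to 40%, over-called in 5 to 20%, T error up to 20%). That compares with 1.09 and 1.18 for surgical stage in both arms at the two downstaging levels. If downstaging is rare, staging error could offset much of the gain.
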